### **Study Design:**

We will conduct a prospective, double-blinded, randomized, non-inferiority, parallel 1:1 clinical trial of 80 children in a single urban pediatric ED. We will block randomize patients to receive either IN ketorolac (1 mg/kg) and an IV placebo (study group A), or IV ketorolac (0.5 mg/kg, maximum single dose of 30 mg) and an IN placebo (study group B). The volume of the IN placebo will be the same volume the patient would have received if they were receiving IN ketorolac; similarly, the volume of IV placebo will be the same volume the patient would have received if they were receiving IV ketorolac. Normal saline will be used as the placebo for both IN and IV administration. IN administration will be performed in a standardized fashion using a mucosal atomization device (MAD), which is a small plastic device that attaches to the end of a syringe.(47) The MAD converts any solution that is expressed from the syringe through the MAD into an atomized spray that is more readily absorbed and easier to deliver than if the solution was given as drops. All patients will receive an IV line to receive IV fluids as is typical in our ED.

The permuted, block randomization scheme will be predetermined by a third-party uninvolved with any study procedures (KB) using an online randomization program. Study group assignment will be concealed in sequentially-numbered sealed opaque envelopes which will not be opened until a patient has been enrolled. The members of the study team performing the pain assessments, those conducting the 24-hour follow up call, and the patient, will all be blinded to the study group assignment.

The chosen dosage and maximum dose of IV ketorolac are the standard of care for children.(48- 50) The maximum single dose of ketorolac which has been administered by the IN route is 30 mg; this is the maximum single dose of IV ketorolac, as well as the maximum dose of IN ketorolac that has been studied in both adults and children.(3,51) This practice is also consistent with the dosing of other IN sedatives and analgesics, in which the maximum single dose given by the IN route is the same as the as that given by the IV route.(12) The dosage of 1 mg/kg for IN ketorolac was selected based on rationale as explained as follows:

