**Study Procedures:** We will assess the patient's pain in a standardized fashion using the FPS-R, administered in the patient's primary language. We will assess the FPS-R and vNRS at baseline (within 15 minutes prior to receiving the study drug) and then at 10 minutes, 30 minutes, and 60 minutes (or within 5 minutes of each mark to allow for unpredictable setting of the emergency department) after administration of the study drug for 60 minutes. We will assess pain associated with nasal administration using the same two scales within 15 minutes of study drug administration. The patient will then be assessed at 2 hours (or within 10 minutes) after administration of the study drug and at 24 hours after study drug administration. Pain assessment not required if a valid documented reason is provided. Such reasons may include, but are not limited to: patient is asleep, having a procedure done, or other medically indicated reason that prohibits a pain assessment from being performed. The Data Collection Form will serve as source document for study drug administration time. The Study Physician will sign on the Data Collection Form as a witness.

If the 24-hour mark is during a timeframe that is inconvenient for the patient (e.g. during sleeping hours), the assessment will be made at a point greater than, but as close to as possible to, the 24-hour mark, within 48-hours of study drug administration. We will conduct the 24-hour follow up by telephone if the patient is discharged from the ED, or in person if the patient is hospitalized (the decision to hospitalize will not be dictated by the study). Patients will be reimbursed \$10 for the time and effort spent participating in this study.

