**Outcomes: Primary Aim:** To demonstrate that IN ketorolac is non-inferior to IV ketorolac in reducing pain in children with acute migraine headaches, we will compare the mean decrease in pain score of both study groups at 60 minutes after administration of the study drug to each other. The outcome we will use to measure this decrease in pain will be the Faces Pain Scale – Revised (FPS-R). The FPS-R is a 10 point pain scale that has been validated for the use in children greater than 4 years of age in the ED; is one of the self-report measures of pain recommended for research in children; and is commonly used as the primary outcome in ED research.(56,57) IN ketorolac will be considered non-inferior to IV ketorolac if the difference between the mean decreases in pain score of both groups is less than a clinically meaningful difference in pain. The minimum clinically meaningful difference in pain in children when using the FPSR has been shown to be 2 out of 10, and is consistent across all categories of age, sex, ethnicity, and primary language; (58) therefore, the non-inferiority margin (delta) will be set at 2/10. In addition to the FPS-R, we will also assess pain using a descriptive ordinal scale frequently used in headache research.(59) Using this scale, we will ask the patient to describe their headache pain as severe, moderate, mild, or none. We will also use the verbal numeric rating scale (vNRS), which involves asking the patient how much pain they have on a scale from zero to ten. We selected the reduction in pain, rather than pain freedom as recommended by the IHS guidelines, as pain freedom is very seldom achieved in the ED, with only approximately 20% of patients reportedly being pain free upon discharge. (59-61) Prior comparative trials of abortive migraine and headache therapies in the ED have similarly shown that as few as 15% of adults and 7% of children achieve headache freedom after treatment, but greater than 60% experience headache relief.(40,62) As a result, pain freedom from migraine or headaches has been infrequently used as the primary outcome for studies in the ED setting; instead, degree of pain relief has been used.(37-40,63-66) Additionally, we chose the one hour end point based on the IHS recommendations that a time point earlier than two hours should be considered for parenteral study medications (which would apply to both IV and IN routes).(59)

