### **Statistical Procedures:**

We will enroll 80 children (40 in each group) ages 8 to 18 years. We based our sample size on the ability to demonstrate non-inferiority between the IN and IV ketorolac groups' ability to reduce pain. It has been shown that a reduction of 2 on the FPS-R score is the minimum clinically significant difference in pain in children. Therefore, our predetermined margin of non-inferiority is 2. In order to be conservative for the sample size calculation, we based the calculation on a margin of 10% less than our predetermined margin of non-inferiority of 2. The resulting sample size of 80 children, therefore, is based on a margin of 1.8 on the FPS-R pain scale. Using a standard deviation of 2.725 (again, selected using conservative assumptions), a sample size of 40 patients per group provides 90% power to detect non-inferiority using a one-sided two sample t-test with an alpha of 0.05.

We will conduct an intention to treat analysis for all enrolled randomized subjects. We will conduct a one-sided t-test to evaluate the difference between the mean decreases in pain score of the two study groups (primary outcome). The difference between groups, with its 95% CI, will be compared to the pre-determined non-inferiority margin (i.e. 2/10) to establish whether IN ketorolac is noninferior to IV ketorolac. For our secondary outcome (time to clinically significant reduction in pain), we will also compare groups using a two-sample one-

sided t-test. Similar to the analysis for the primary outcome, the difference between groups in the time to clinically significant reduction in pain, with its 95% CI, will be compared to the pre-determined non-inferiority margin of 10 minutes. A Kaplan-Meier distribution analysis will also be used to compare the time to meaningful pain relief in the two treatment groups. For other secondary outcomes, we will compare groups using standard bivariate analyses for categorical and continuous variables and a table describing adverse events by treatment will be reported.

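### The primary analysis is an unadjusted t-test on the 60-minute FPS-R decrease; prespecifying baseline FPS-R as a covariate before unblinding may gain precision, at a worst-case cost of about 0.4 points of power.

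*Combined protocol and SAP*

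**What the plan says.** The Outcomes paragraph defines the primary contrast on the FPS-R: the investigators will "compare the mean decrease in pain score of both study groups at 60 minutes after administration of the study drug". Statistical Procedures sets the test: "We will conduct a one-sided t-test to evaluate the difference between the mean decreases in pain score of the two study groups". It then gives the decision rule: "The difference between groups, with its 95% CI, will be compared to the pre-determined non-inferiority margin (i.e. 2/10".

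The sizing statement reads "Using a standard deviation of 2.725 (again, selected using conservative assumptions), a sample size of 40 patients per group provides 90% power", "using a one-sided two sample t-test with an alpha of 0.05". The sizing margin is 1.8 and the decision margin is 2.

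The baseline value is already part of the schedule. Study Procedures states "We will assess the FPS-R and vNRS at baseline (within 15 minutes prior to receiving the study drug". Study Design describes permuted blocks and names no stratification factor, so baseline pain is not balanced by design. No covariate-adjusted model is named for any outcome; the other secondary outcomes are to be compared by bivariate methods.

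**The concern.** Analysing the decrease is not the same as adjusting for baseline. The decrease is the baseline score minus the 60-minute score, so it fixes the slope of the 60-minute score on baseline at 1 instead of estimating it. If the true slope is below or above 1, the decrease still depends on the baseline score. That has one cost, which can be seen in two ways: the interval is wider than it need be, and part of any chance baseline difference between the arms stays in the estimate. The t-test's interval already allows for such imbalance over repeated randomisations, so this is lost efficiency and not bias.

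It is worth attention here because the conclusion depends on whether one confidence limit falls inside a margin of 2, with 80 children at a single site. A baseline covariate can narrow that interval without adding a child or an assessment. In a linear model, the difference in means and its margin keep their meaning.

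**Working it through.** **Inputs from the documents.** 40 per group; SD 2.725; sizing margin 1.8 at one-sided alpha 0.05; decision margin 2. The decision rule can be read as a two-sided 95% CI (one-sided 0.025) or as the one-sided 0.05 test, so both are shown.

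**Assumptions.** The true difference is 0, data are normal, and all 80 children are analysed. The documents do not say that 2.725 is the SD of the decrease; I take it to be. They give no baseline SD (s0) and no baseline/60-minute correlation (rho); I use s0 of 1.5 and 2.0 and rho of 0.2 to 0.6.

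**Step 1: the plan's own figure.** SE = 2.725 × √(2/40) = 0.609. The noncentrality is 1.8/0.609 = 2.95 on 78 df, and power at one-sided 0.05 is 90.03%. The stated 90% reproduces. At the decision margin of 2, unadjusted power is 90.0% (one-sided 0.025) or 94.6% (one-sided 0.05). The two-sided 95% half-width is 1.21.

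**Step 2: worst-case cost of the covariate.** This arises when the slope is exactly 1, so that baseline does not predict the decrease. Estimating the slope multiplies the expected variance by 1 + 1/(80 − 4) = 1.013 and leaves 77 df.

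| Margin, one-sided alpha | Unadjusted | Adjusted | Loss (points) |
|---|---|---|---|
| 2, 0.025 | 90.00% | 89.62% | 0.39 |
| 2, 0.05 | 94.62% | 94.38% | 0.24 |
| 1.8, 0.05 (sizing inputs) | 90.03% | 89.69% | 0.34 |

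Losses are from unrounded powers. Nearly all of the loss comes from chance baseline imbalance; the lost degree of freedom alone costs about 0.01 points.

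**Step 3: range of results.** Solve for the 60-minute SD, s1, from s0² + s1² − 2·rho·s0·s1 = 2.725². The slope is b = rho·s1/s0. The net variance ratio is s1²(1 − rho²) × 1.013 / 2.725².

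Example with s0 = 2.0 and rho = 0.2: s1 = 2.294, b = 0.229, residual variance 5.05, and ratio 5.05 × 1.013 / 7.426 = 0.689.

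The last column is the shift in the unadjusted contrast from a 2-SE baseline imbalance (about 1 trial in 20): (1 − b) × 2 × s0 × √(2/40).

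| s0 | rho | Slope b | Variance ratio | Power, margin 2, 0.025 | Power, margin 2, 0.05 | 95% half-width | Shift |
|---|---|---|---|---|---|---|---|
| 1.5 | 0.2 | 0.346 | 0.882 | 93.2% | 96.6% | 1.14 | 0.44 |
| 1.5 | 0.3 | 0.554 | 0.952 | 91.3% | 95.4% | 1.18 | 0.30 |
| 1.5 | 0.4 | 0.787 | 0.999 | 90.0% | 94.6% | 1.21 | 0.14 |
| 1.5 | 0.5 | 1.048 | 1.012 | 89.6% | 94.4% | 1.22 | −0.03 |
| 1.5 | 0.6 | 1.339 | 0.978 | 90.6% | 95.0% | 1.20 | −0.23 |
| 2.0 | 0.2 | 0.229 | 0.689 | 97.4% | 98.9% | 1.01 | 0.69 |
| 2.0 | 0.3 | 0.382 | 0.805 | 95.1% | 97.6% | 1.09 | 0.55 |
| 2.0 | 0.4 | 0.563 | 0.909 | 92.5% | 96.1% | 1.16 | 0.39 |
| 2.0 | 0.5 | 0.776 | 0.986 | 90.4% | 94.9% | 1.21 | 0.20 |
| 2.0 | 0.6 | 1.022 | 1.013 | 89.6% | 94.4% | 1.22 | −0.02 |

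**Step 4: break-even.** The variance falls only if |1 − b| exceeds √(1 − 1/1.013) × 2.725/s0, which is about 0.21 for s0 = 1.5 and 0.16 for s0 = 2.0.

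**Step 5: simulation.** Four cells of the table, at 100,000 trials each, agreed with the analytic powers to within about 0.1 point. Separate runs at margin 1.8 gave type I error close to nominal for both analyses (about 0.051 at 0.05 and 0.025 at 0.025).

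**The case against.** The strongest objection is that nothing is broken. The t-test is valid, answers the stated question on the scale of the margin, and has its stated power. The documents supply neither the baseline SD nor the correlation, so they cannot show that any gain exists. In half the cells above, power at one-sided 0.025 changes by only −0.4 to +0.6 points, and the largest figures come from one corner (s0 = 2.0, rho = 0.2). Study Subjects also sets a baseline pain threshold of 4/10, which may narrow the baseline spread and so limit the gain. All of this stands, and it is why the claim is limited to a possible gain.

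The plan also has slack. It sizes at 1.8 but decides at 2, and calls its SD conservative. At a true SD of 2.5, unadjusted power at margin 2 is already 94.2% (two-sided 95% CI) or 97.1% (one-sided 0.05). This reduces the power left to gain. It does not remove the narrower interval or the protection against baseline imbalance.

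The worst-case cost is an average over randomisations. With a slope of 1 and a realised 2-SE imbalance, the variance multiplier is 1 + 4/78 = 1.05, and power at margin 2 under a two-sided 95% CI would be about 88.5%. That is true, but power is by definition such an average, and the worst case here is over the unknown slope. A loss of 0.50 points appears only if the sizing margin of 1.8 is paired with one-sided 0.025, which is not the decision rule.

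Finally, Study Procedures allows pain assessments to be skipped for documented reasons, and no inflation for this is stated. The absolute powers and half-widths are therefore optimistic, for both analyses.

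**Conclusion.** The point holds as an improvement, not as the correction of an error. At the decision margin of 2, the most that prespecifying baseline FPS-R can be expected to cost is about 0.4 points of power under a two-sided 95% CI, or about 0.2 under the one-sided 0.05 test. Under the assumed inputs, the best case is a gain of 7.4 points (90.0% to 97.4%) or 4.3 points (94.6% to 98.9%), with the half-width falling from 1.21 to 1.01. The same best case would remove a shift of up to 0.69 points, about a third of the margin, caused by a 2-SE baseline imbalance; such a shift can favour either arm.

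The cost side follows from the plan's own numbers, with 2.725 taken as the SD of the decrease. The gain side also depends on a baseline SD and a correlation that the documents do not give. There is no gain if the true slope is close to 1.

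**What to change.** In Statistical Procedures, before unblinding, name as the primary analysis a linear model of the 60-minute FPS-R decrease on treatment with baseline FPS-R as covariate. Compare the confidence limit of the adjusted treatment difference with the margin of 2, and keep the unadjusted t-test as a supporting analysis. The documents do not say whether the data are still blinded. If they are not, the t-test should stay primary and the adjusted result be reported only as a sensitivity analysis.

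The cost is one or two sentences, one degree of freedom and the power cost given above. The change also has to go to the IRB, because Data and Safety Monitoring says that protocol modifications are submitted there. It needs no new data. A child without a baseline score has no decrease under either analysis, so adjustment loses no further child.

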IN ketorolac administration may allow children to receive effective analgesia in an expeditious and painless manner in the ED, as well as in a broader number of settings. The implementation of IN medications decreases the time it takes for a child to receive analgesics in the ED compared to those receiving IV analgesics, as the IN route does not require the additional, technically more challenging step of obtaining IV access.(22) Effective analgesics such as ketorolac are typically administered by the IV and IM route and require children to receive a painful needle stick, an experience that has been identified by them as amongst the medical experiences that they most fear, causing high levels of pain and distress.(23-28) The IN route is a completely needle-free technique, and saves children from both the short and long term consequences of inadequately managed needle stick pain.(29-33) Finally, eliminating the need for IV access to administer analgesics creates the potential opportunity for children to receive more potent and effective analgesics at home or in the office setting, rather than the hospital.

Our overall goal is to determine best-practice management of children with acute migraines. Our specific aims for this study are as follows:

**Primary Aim:** Determine whether intranasal (IN) ketorolac is non-inferior to intravenous (IV) ketorolac for reducing pain in children with acute migraine headaches. We hypothesize that IN ketorolac is non-inferior to IV ketorolac in reducing acute migraine headache pain by a minimum clinically significant difference within 60 minutes of administration.

**Secondary Aim:** Determine whether there is a difference in the time to achieve a clinically significant reduction in pain after receiving IN ketorolac compared to IV ketorolac. We hypothesize that there is no difference between groups in the time it takes to achieve a clinically significant reduction in pain. If we can demonstrate that IN ketorolac is as efficacious as IV ketorolac, this would support the clinical implementation of this novel modality for effectively treating migraine pain, in addition to incurring additional benefits (such as eliminating

unnecessary needle pain and decreasing time to receiving analgesics) that would improve the overall care of children with migraines.

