Secondary Aim: To determine if there is a difference in time to achieve a clinically significant reduction in pain after receiving IN ketorolac compared to IV ketorolac, we will use the outcome of time (in minutes) and compare, as appropriate, the mean or median time it takes after administration of study drug in each group to achieve a minimum clinically significant difference in pain (i.e. 2/10 on the FPS-R).

Note that a prior iteration of the protocol stated that this secondary aim was to determine if IN ketorolac was non-inferior to IV ketorolac, with a non-inferiority margin for this aim of 10 minutes. This secondary aim was changed prior to starting patient enrollment (i.e. no patients were enrolled yet) because the number of pain assessments was decreased from assessments at 10, 20, 30, 40, 50, 60, and 120 minutes to 10, 30, 60, and 120 minutes for feasibility reasons. Since we would then no longer be able to assess change in pain score in 10 minute increments, it would not have been possible to accurately assess for non-inferiority based on a non-inferiority margin of 10 minutes. Therefore, the aim was changed to as is currently stated.

Additional efficacy outcomes will include those that are ED-based, and those assessed at a 24- hour follow up:

- i) ED-based outcomes: 1) Receipt of rescue medications at any time during the ED visit; 2) Headache relief in the ED, defined as change within 2 hours of the patient's description of headache from severe or moderate to either mild or none, on the severe/moderate/mild/none pain scale, without the use of rescue medications; 3) Headache freedom in the ED, defined as achieving a headache level of none within 2 hours without the use of rescue medications; and 4) Percentage improvement in pain score between baseline and one hour, defined as (baseline pain score – one hour pain score)/baseline pain score.

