### **Potential Risks:**

There are no risks in addition to the usual risks associated with receiving ketorolac for analgesia. There is a chance that a patient may not experience the same degree of pain relief that they may have experienced if they had received IV ketorolac. However, patients will have their pain assessed as per usual standard care, and can receive any additional required analgesics at any point in time if their pain relief is inadequate. The procedures involved in this study do not increase the risk for adverse events normally associated with receiving ketorolac.

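### Statistical Procedures still tests time to pain relief one-sided against a 10-minute non-inferiority margin that the protocol says was given up before enrolment

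*Combined protocol and SAP*

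**What the plan says.** Study Purpose and Rationale gives the secondary aim as: "Determine whether there is a difference in the time to achieve a clinically significant reduction in pain after receiving IN ketorolac compared to IV ketorolac". The hypothesis beside it is that the times do not differ. The Secondary Aim paragraph of the Outcomes text repeats this aim, proposes to compare mean or median times as appropriate, and gives no margin.

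That paragraph also explains a change made before any child was enrolled. The aim had been non-inferiority with a 10-minute margin. For feasibility, "the number of pain assessments was decreased from assessments at 10, 20, 30, 40, 50, 60, and 120 minutes". Four were kept: those at 10, 30, 60 and 120 minutes. The stated consequence is that "it would not have been possible to accurately assess for non-inferiority based on a non-inferiority margin of 10 minutes". Study Procedures uses the reduced schedule.

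For the same outcome, Statistical Procedures prescribes a two-sample one-sided t-test and says the group difference, "with its 95% CI, will be compared to the pre-determined non-inferiority margin of 10 minutes". It then adds: "A Kaplan-Meier distribution analysis will also be used to compare the time to meaningful pain relief in the two treatment groups". No test, sidedness or alpha is given for that second analysis. The section opens its analysis text with: "We will conduct an intention to treat analysis for all enrolled randomized subjects".

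**The concern.** The analysis section answers a question that the protocol no longer asks. An analyst working from it would declare IN ketorolac non-inferior, or not, on time to relief, using a margin that the same document says its data cannot assess accurately. The only named test for this outcome looks in one direction, while the aim is a difference in either direction.

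Two gaps add to this:

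- A t-test needs a time for every child. None is defined for a child who never reaches the 2-point fall. Dropping those children would restrict the comparison to responders, against the intention-to-treat statement.
- Potential Risks says that patients "can receive any additional required analgesics at any point in time" if relief is inadequate. Headache relief and headache freedom are defined as being without rescue medication. The time outcome is silent on whether a fall after rescue counts.

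**Working it through.** **1. The plan's own figure.** The only sample-size calculation is for the primary outcome: margin 1.8, SD 2.725, one-sided alpha 0.05, 90% power.

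n per group = 2 × (1.645 + 1.282)² × 2.725² / 1.8² = 2 × 8.57 × 7.43 / 3.24 ≈ 39.3, so 40. Exact power at 40 per group from the noncentral t distribution is 90.0%. The plan's figure reproduces, and it does not involve the time outcome.

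**2. The texts side by side.**

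| Item | Study Purpose and Outcomes text | Statistical Procedures |
|---|---|---|
| Question | Is there a difference? | Is IN non-inferior? |
| Margin | None; 10 minutes belonged to a prior iteration | 10 minutes |
| Direction | Either | One-sided test |

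This is not a log entry set against current text. The superseded rule stands in the operative analysis section.

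**3. What the schedule does to a 10-minute delay.** Inputs are the two schedules in the Outcomes text: older 10, 20, 30, 40, 50, 60, 120 minutes; present 10, 30, 60, 120 minutes. Assume that each assessment falls exactly on its mark and that the recorded time is the first assessment at or after true relief. Let a child's relief time be t on IV and t + 10 on IN.

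| True IV time t (min) | Older schedule: IV, IN, difference | Present schedule: IV, IN, difference |
|---|---|---|
| 0–10 | 10, 20, **10** | 10, 30, **20** |
| 10–20 | 20, 30, **10** | 30, 30, **0** |
| 20–30 | 30, 40, **10** | 30, 60, **30** |
| 30–40 | 40, 50, **10** | 60, 60, **0** |
| 40–50 | 50, 60, **10** | 60, 60, **0** |
| 50–60 | 60, 120, **60** | 60, 120, **60** |
| 60–110 | 120, 120, **0** | 120, 120, **0** |

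**4. Group means on the present schedule.** The older schedule gives 10 minutes in every line below.

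- IV times even over 0–50: (10×20 + 10×0 + 10×30 + 20×0) / 50 = 10.0 minutes.
- Even over 0–30: (10×20 + 10×0 + 10×30) / 30 = 16.7 minutes.
- Even over 10–50: (10×0 + 10×30 + 20×0) / 40 = 7.5 minutes.
- Even over 30–50: 0 minutes.

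The distortion can go either way or cancel, depending on where the times fall. The documents give no distribution or SD for time, so no error rate for the test can be derived.

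**5. Assessment windows.** Study Procedures allows each assessment in the first hour to fall within 5 minutes of its mark. Two children scored at the same nominal visit can therefore differ by up to 5 + 5 = 10 minutes, as much as the margin itself.

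**The case against.** The strongest reply is that the document settles the matter itself. The Outcomes text says which aim is current, when it changed and why, so a wrong verdict would require the team to overlook its own explanation. The outcome is secondary, and the leftover is a stale sentence. This limits the weight of the point but does not remove it: the statistical section is what an analyst would follow, and it still states the rule.

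Some further points stand:

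- The planned 95% CI can be read against zero in both directions. Only the one-sided test and the comparison with the margin are off the aim.
- The Kaplan-Meier analysis can accommodate children who never reach the threshold, by censoring them. The missing-value problem belongs to the t-test.
- The schedule arithmetic is not needed to establish the contradiction. It only illustrates the reason the protocol already gives.
- A restricted mean calculated from recorded visit times carries the same rounding as a simple mean. Only a method that treats the times as interval-censored deals with it.

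It might also be said that a time-to-event analysis departs from the mean-or-median comparison in the Outcomes text. It does not: a Kaplan-Meier median or a restricted mean fits that wording.

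**Conclusion.** The concern holds. Statistical Procedures contradicts the current secondary aim by keeping a one-sided test and a margin that the protocol has given up. The contradiction rests on the text alone and needs no assumption.

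The illustration of size assumes on-the-mark assessments: a true 10-minute delay is recorded as 0, 20 or 30 minutes for IV times up to 50 minutes. The group mean can be overstated (16.7), understated (7.5 or 0) or unchanged (10.0). No failure rate is claimed.

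This should be fixed, but it does not threaten the trial. The primary analysis, its margin of 2 and the 80 children are unaffected.

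**What to change.** The necessary change, in Statistical Procedures for time to clinically significant reduction in pain:

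- Delete the one-sided t-test and the 10-minute margin.
- Make the Kaplan-Meier analysis the stated analysis, with a two-sided log-rank test at alpha 0.05. An interval-censored test would respect the 10, 30, 60 and 120 minute visits better.
- Report a between-group difference with a 95% CI, for example in restricted mean time to 120 minutes. If it is calculated from recorded visit times, say that it carries the rounding shown above.
- Keep all randomised children. Censor those who do not reach the 2-point fall at their last assessment within the 120 minutes.

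Useful additions, on which the point does not depend:

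- State in advance whether a fall after rescue medication counts, and report the other choice as a sensitivity analysis.
- State that a non-significant result will not be read as showing equal times, since the hypothesis is one of no difference.

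The deletion costs wording only, and the sponsor gives up nothing that the Outcomes text has not already given up. The censoring and rescue rules are small analytic decisions to write down; they need no more children and no more pain assessments. If the analysis has already been run, document which rule was used and do not report a non-inferiority verdict on time.
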